#### **9.2.3      Safety Assessments**

Planned time points for all safety assessments are listed in the Schedule of Activities see (Table 2-1).

##### **9.2.3.1      Adverse Events**

###### **9.2.3.1.1      Time Period and Frequency for Collecting and Reporting Safety Event Information**

###### **9.2.3.1.1.1      Adverse Events**

The adverse event grading scale to be used for this study will be the Common Terminology Criteria for Adverse Events (CTCAE) and is described in Section 12.4.

The investigator is responsible for ensuring that all adverse events observed by the investigator or reported by the subject that occur after signing of the ICF through 30 (+3) days after the last dose of all study drug(s) are reported using the Event eCRF.

###### **9.2.3.1.1.2      Serious Adverse Events**

The investigator is responsible for ensuring that all serious adverse events observed by the investigator or reported by the subject that occur after signing of the ICF through 30 (+3) days after the last dose of all study drug(s) are reported using the Event eCRF.

All serious adverse events will be collected, recorded and reported to the sponsor or designee within 24 hours, as indicated in Section 12.4. The investigator will submit any updated serious adverse event data to the sponsor within 24 hours of it being available.

The criteria for grade 4 in the CTCAE grading scale differs from the regulatory criteria for serious adverse events. It is left to the investigator's judgment to report these grade 4 abnormalities as serious adverse events.

#### **9.2.3.1.1.3 Serious Adverse Events After the Protocol-required Reporting Period**

If the investigator becomes aware of serious adverse events suspected to be related to IP or fatal serious adverse events (regardless of causality) after completion of the protocol-required reporting period (as defined in Section 9.2.3.1.1.2), then these serious adverse events will be reported to Amgen within 24 hours following the investigator's awareness of the event on the Events CRF.

After End of Study, there is no requirement to actively monitor study subjects after the study has ended with regards to study subjects treated by the investigator. However, if the investigator becomes aware of serious adverse events suspected to be related to investigational product, then these serious adverse events will be reported to Amgen within 24 hours following the investigator's awareness of the event.

Serious adverse events reported outside of the protocol-required reporting period will be captured within the safety database as clinical trial cases and handled accordingly based on relationship to investigational product.

If further safety related data is needed to fulfill any regulatory reporting requirements for a reportable event, then additional information may need to be collected from the subject's records after the subject ends the study.

The method of recording, evaluating, and assessing causality of adverse events, and serious adverse events and the procedures for completing and transmitting serious adverse event reports are provided in Section 12.4.

#### **9.2.3.1.2 Method of Detecting Adverse Events and Serious Adverse Events**

Care will be taken not to introduce bias when detecting adverse events and/or serious adverse events. Open-ended and non-leading verbal questioning of the subject is the preferred method to inquire about adverse event occurrence.

#### **9.2.3.1.3 Follow-up of Adverse Events and Serious Adverse Events**

After the initial adverse event/serious adverse event report, the investigator is required to proactively follow each subject at subsequent visits/contacts. All adverse events and serious adverse events will be followed until resolution, stabilization, until the event is otherwise explained, or the subject is lost to follow-up (as defined in Section 8.3).

Further information on follow-up procedures is given in Section 12.4.

All new information for previously reported serious adverse events must be sent to Amgen within 24 hours following knowledge of the new information. If specifically requested, the investigator may need to provide additional follow-up information, such as discharge summaries, medical records, or extracts from the medical records.

Information provided about the serious adverse event must be consistent with that recorded on the Event eCRF.

#### **9.2.3.1.4 Regulatory Reporting Requirements for Serious Adverse Events**

If subject is permanently withdrawn from protocol-required therapies because of a serious adverse event, this information must be submitted to Amgen.

Prompt notification by the investigator to the sponsor of serious adverse events is essential so that legal obligations and ethical responsibilities towards the safety of subjects and the safety of a study treatment under clinical investigation are met.

The sponsor has a legal responsibility to notify both the local regulatory authority and other regulatory agencies about the safety of a study treatment under clinical investigation. The sponsor will comply with country-specific regulatory requirements relating to safety reporting to the regulatory authority, IRBs/IECs, and investigators.

Individual safety reports must be prepared for suspected unexpected serious adverse reactions according to local regulatory requirements and sponsor policy and forwarded to investigators as necessary.

An investigator who receives an individual safety report describing a serious adverse event or other specific safety information (eg, summary or listing of serious adverse events) from the sponsor will file it along with the IB and will notify the IRB/IEC, if appropriate according to local requirements.

#### **9.2.3.1.5 Safety Monitoring Plan**

Subject safety will be routinely monitored as defined in Amgen's safety surveillance and signal management process.

#### **9.2.3.1.6      Pregnancy and Lactation**

Details of all pregnancies and/or lactation in female subjects and female partners of male subjects will be collected after the start of study treatment and until 30 days (for female subjects) and 90 days (for female partners of male subjects) after the last dose of all study drug(s).

If a pregnancy is reported, the investigator is to inform Amgen within 24 hours of learning of the pregnancy and/or lactation and is to follow the procedures outlined in Section 12.5. Amgen Global Patient Safety will follow-up with the investigator regarding additional information that may be requested.

Abnormal pregnancy outcomes (eg, spontaneous abortion, fetal death, stillbirth, congenital anomalies, ectopic pregnancy) are considered serious adverse events.

Further details regarding pregnancy and lactation are provided in Section 12.5.

#### **9.2.3.2      Vital Signs**

The following measurements must be performed: systolic/diastolic blood pressure, heart rate, respiratory rate, and temperature.

Subject must be in a supine position in a rested and calm state for at least 5 minutes before blood pressure assessments are conducted. If the subject is unable to be in the supine position, the subject should be in most recumbent position as possible. The position selected for a subject should be the same that is used throughout the study and documented on the vital signs eCRF. Take 3 blood pressure measurements spaced 1 to 2 minutes apart and additional measurements if the first 2 are more than 10 mmHg apart for either systolic or diastolic blood pressure (see Section 12.10).

The temperature location selected for a subject should be the same that is used throughout the study and documented on the vital signs eCRF.

#### **Additional Vital Sign Measurements**

In cycles 1 and 6, an additional blood pressure measurement post-carfilzomib infusion will be collected (within 30 minutes of the end of infusion).

Record all measurements on the vital signs eCRF. For blood pressure, record the average blood pressure.

#### **9.2.3.3      Electrocardiograms (ECGs)**

Subject must be in supine position in a rested and calm state for at least 5 minutes before ECG assessment is conducted. If the subject is unable to be in the supine

position, the subject should be in most recumbent position as possible. The ECG must include the following measurements: heart rate, QRS, QT, QTc, and PR intervals. The principal investigator or (eg, designated site physician, central reader) will review all ECGs. Once signed, the original ECG tracing will be retained with the subject's source documents. At the request of the sponsor, a copy of the original ECG will be made available to Amgen.

Electrocardiograms will be required in all subjects at screening. Electrocardiogram monitoring is required on cycle 1 day 8 and cycle 2 day 1 at the end of the carfilzomib infusion, and as clinically indicated.

#### **9.2.3.4 Other Safety**

##### **9.2.3.4.1 Echocardiogram**

All subjects will have a baseline ECHO, including assessments of systolic and diastolic left ventricular function and right ventricular function. Screening ECHO may be done within 30 days prior to randomization, if performed as a part of standard of care.

Echocardiogram is to be repeated approximately every 6 months ( $\pm$  2 weeks) from cycle 1 day 1 until safety follow-up visit, and additionally, if clinically indicated. An ECHO must be performed within 72 hours of the onset of a cardiac failure event.

##### **9.2.3.4.2 Pulmonary Function Tests (PFTs)**

Baseline and surveillance pulmonary function tests are may be performed if clinically indicated at the discretion of the investigator.

##### **9.2.3.4.3 Hepatitis B**

All hepatitis testing will be performed locally. All subjects will be tested at screening for hepatitis B surface antigen (HBsAg), hepatitis B surface antibody (anti-HBs), and hepatitis B core antibody (anti-HBc), unless performed within 6 months of screening and there was no change in the subject's risk factors within these 6 months.

Subjects with no history of HBV infection that are negative for hepatitis serologies at screening should be followed as clinically indicated.

Subjects with positive testing or who have a prior history of HBV infection should have consultation with a specialist in HBV and have HBV DNA testing and monitoring of HBV DNA every 12 weeks ( $\pm$  2 weeks) or more frequently, if clinically indicated, through safety follow-up. Subjects that have received hepatitis B vaccination with only anti-HBs positivity and no clinical signs of hepatitis do not require HBV DNA monitoring.

Any subject who becomes HBV DNA positive or develops reactivation of HBV will have study treatment interrupted and receive appropriate antiviral treatment as per a specialist in hepatitis B. Resumption of clinical study therapy may be considered in subjects whose HBV reactivation is controlled and where the benefits of clinical study therapy outweigh the risks. After cessation of study therapy for any reason, any ongoing monitoring and antiviral treatment should be under the guidance of a specialist in HBV.

#### **9.2.4 Clinical Laboratory Assessments**

Refer to Section [12.2](#) for the list of clinical laboratory tests to be performed and to the Schedule of Activities ([Table 2-1](#)) for the timing and frequency.

The investigator is responsible for reviewing laboratory test results and recording any clinically relevant changes occurring during the study in the Event eCRF. The investigator must determine whether an abnormal value in an individual study subject represents a clinically significant change from the subject's baseline values. In general, abnormal laboratory findings without clinical significance (based on the investigator's judgment) are not to be recorded as adverse events. However, laboratory value changes that require treatment or adjustment in current therapy are considered adverse events. Where applicable, clinical sequelae (not the laboratory abnormality) are to be recorded as the adverse event.

All protocol-required laboratory assessments, as defined in Section [12.2](#), must be conducted in accordance with the laboratory manual and the Schedule of Activities ([Table 2-1](#)).

##### **9.2.4.1 Pregnancy Testing**

A serum pregnancy test must be completed at screening (10 to 14 days prior to cycle 1 day 1). A serum or urine pregnancy test must be completed within 24 hours of initiation of lenalidomide for FCBP. Additional pregnancy testing must also be performed during treatment, as per Schedule of Activities ([Table 2-1](#)) and at the safety follow-up visit.

Note: Females who have undergone a bilateral tubal ligation/occlusion do not require pregnancy testing per protocol requirements. (If a female subject, or the partner of a male subject, becomes pregnant it must be reported on the Pregnancy Notification Form, see [Figure 12-2](#)). Refer to Section [12.5](#) for contraceptive requirements.

Additional on-treatment pregnancy testing may be performed at the investigator's discretion or as required per local laws and regulations.

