**Table 2-1. Schedule of Activities**

PROCEDURE	Scree ning a (up to 28 days before rand)	Treatment Period Cycles 1 to 12							Safety FU (30 [+3] days after last dose)	LTFU b (every 28 ± 7 days)	Notes
		Day 1	2	8	9	15	16	22			
Survival										(X)	Subjects who terminate early from study treatment (less than 12 complete cycles) will be followed every 28 ± 7 days after safety follow-up visit until 12 months after randomization, death, loss to follow-up or withdrawal of full consent, whichever comes first.
Subsequent antimyeloma therapies										(X)	All subjects who have ended study treatment without a confirmed PD will be followed every 28 ± 7 days until 12 months after randomization, first subsequent antimyeloma, death, loss to follow-up, withdrawal of full consent, or confirmed PD, whichever comes first.
Adverse events/serious adverse events c		Continuous									
Concomitant therapies review		Continuous									
LABORATORY ASSESSMENTS											
Pregnancy test (FCBP only)	Serum	X						X		At screening: 10 to 14 days prior to C1D1	
	Urine or serum cycle 1 (predose)		X	X		X		X		Within 24 hours prior to dose of lenalidomide.	
	Urine or serum cycle 2 to 12 (predose; regular menses)		X								
	Urine or serum cycle 2 to 12 (irregular menses)		X			X					
Hematology		X	X						X		Hematology and chemistry samples from screening may be used for C1D1 if taken within 3 days prior to C1D1. Hematology and chemistry samples taken within 48 hours of D1 of subsequent cycles may be used for treatment decisions. Laboratory results must be evaluated for potential dose modification assessment prior to dosing.
Chemistry		X	X						X		

Footnotes are defined on the last page of the table.

Page 2 of 8

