#### **Other Exclusions**

- 235 Female subject is pregnant or breastfeeding or planning to become pregnant or breastfeed during treatment and for an additional 30 days after the last dose of all study drug(s). (Females of childbearing potential should only be included in

the study after a confirmed menstrual period and a negative highly sensitive urine or serum pregnancy test).

236 Female subjects of childbearing potential unwilling to use 2 methods of contraception (1 highly effective form of contraception and 1 additional effective contraceptive method) for at least 28 days before starting study drug(s), during treatment, during treatment interruptions, and for an additional 30 days after the last dose of all study drug(s). Refer to Section [12.5](#) for additional contraceptive information.

237 Female subjects of childbearing potential with a positive pregnancy test assessed at screening (by a highly sensitive serum pregnancy test 10 to 14 days prior to first dose of study drugs).

238 Male subjects with a female partner of childbearing potential who are unwilling to practice sexual abstinence (refrain from heterosexual intercourse) or use a condom with spermicide during treatment and for an additional 90 days after the last dose of all study drug(s), even if they have undergone a successful vasectomy. Refer to Section [12.5](#) for additional contraceptive information.

239 Male subjects with a pregnant partner who are unwilling to practice abstinence or use a condom with spermicide during treatment and for an additional 90 days after the last dose of all study drug(s).

240 Male subjects unwilling to abstain from donating blood, semen, or sperm during treatment and for an additional 90 days after the last dose of all study drug(s).

241 Females subjects unwilling to abstain from donating blood during treatment and for an additional 90 days after the last dose of all study drug(s).

242 Subject likely to not be available to complete all protocol-required study visits or procedures, and/or to comply with all required study assessments (including COA) to the best of the subject and investigator's knowledge.

243 History or evidence of any other clinically significant disorder, condition or disease (with the exception of those outlined above) that, in the opinion of the investigator or Amgen physician, if consulted, would pose a risk to subject safety or interfere with the study evaluation, procedures or completion.

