#### **12.5.3 Definition of Females of Childbearing Potential**

A female is considered fertile after menarche and until becoming postmenopausal unless permanently sterile. Permanent sterilization methods include hysterectomy, bilateral salpingectomy, and bilateral oophorectomy.

Females in the following categories are not considered female of childbearing potential:

- Premenopausal female with 1 of the following:
  - Documented hysterectomy;
  - Documented bilateral salpingectomy; or
  - Documented bilateral oophorectomy.

Note: Site personnel documentation from the following sources is acceptable:

- 1) review of subject's medical records; 2) subject's medical examination; or
- 3) subject's medical history interview.

- Premenarchal female

- Postmenopausal female
  - A postmenopausal state is defined as no menses for 12 consecutive months without an alternative medical cause. A high follicle stimulating hormone (FSH) level in the postmenopausal range may be used to confirm a postmenopausal state in women not using hormonal contraception or hormonal replacement therapy (HRT). However, in the absence of 12 months of amenorrhea, a single FSH measurement is insufficient.
  - Females on HRT and whose menopausal status is in doubt will be required to use 1 of the non-hormonal highly effective contraception methods if they wish to continue their HRT during the study. Otherwise, they must discontinue HRT to allow confirmation of postmenopausal status before study enrollment

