### Highly Effective Contraceptive Methods

Note: Failure rate of < 1% per year when used consistently and correctly.

- combined (estrogen and progestogen containing) hormonal contraception associated with inhibition of ovulation (oral, intravaginal, or transdermal)
- progestogen-only hormonal contraception associated with inhibition of ovulation (oral, injectable, implantable)
- intrauterine device
- intrauterine hormonal-releasing system
- bilateral tubal ligation/occlusion
- vasectomized partner (provided that partner is the sole sexual partner of the female subject of childbearing potential and that the vasectomized partner has received medical assessment of the surgical success)
- sexual abstinence (defined as refraining from heterosexual intercourse during the entire period of risk associated with the study treatments; the reliability of sexual abstinence must be evaluated in relation to the duration of the study and the preferred and usual lifestyle of the subject)

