#### **12.5.5 Pregnancy Testing**

##### **12.5.5.1 Female Subjects**

Medically supervised pregnancy tests with a minimum sensitivity of 50 mIU/mL must be performed for FCBP, including FCBP who commit to complete abstinence, as outlined below.

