**Before starting lenalidomide:**

Female Subjects:

- FCBP must have 2 negative pregnancy tests (sensitivity of at least 50 mIU/mL) prior to starting lenalidomide. The first pregnancy test must be performed within 10 to 14 days prior to the first dose of study drugs and the second pregnancy test must be performed within 24 hours prior to the start of lenalidomide. The subject may not receive lenalidomide until the Investigator has verified that the results of these pregnancy tests are negative.
- Will be warned that sharing study drug is prohibited and will be counseled about pregnancy precautions and potential risks of fetal exposure.
- Must agree to abstain from donating blood during study participation and for at least 90 days after the last dose of all study drug(s).

During study participation and for 30 days after discontinuation from the study:

Female Subjects:

- FCBP with regular menstrual cycles must agree to have pregnancy tests weekly for the first 28 days of study participation and then every 28 days while on study, and 30 [+3] days after the last dose of all study drug(s). If menstrual cycles are irregular, the pregnancy testing must occur weekly for the first 28 days and then every 14 days while on study, 30 [+3] days after the last dose of all study drug(s).
- In addition to the required pregnancy testing, the Investigator must confirm with FCBP that she is continuing to use 2 reliable methods of birth control at each visit.
- Counseling about pregnancy precautions and the potential risks of fetal exposure must be conducted at a minimum of every 28 days and at the time that lenalidomide treatment is discontinued. During counseling, subjects must be reminded to not share study drug and to not donate blood.

- Pregnancy testing and counseling must be performed if a subject misses her period or if her pregnancy test or her menstrual bleeding is abnormal. Lenalidomide treatment must be discontinued during this evaluation.
- Females must agree to abstain from breastfeeding during study participation and for at least 30 days after the last dose of all study drug(s).
- If pregnancy or a positive pregnancy test does occur in a study patient, study drug must be immediately discontinued.

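### Section 9.2.4.1 waives pregnancy testing after tubal ligation, but the rest of the protocol requires testing for the same women before and during lenalidomide

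*Protocol*

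**What the plan says.** Protocol Section 9.2.4.1 sets out pregnancy testing and then adds a note: "Females who have undergone a bilateral tubal ligation/occlusion do not require pregnancy testing per protocol requirements". The same section also states: "Additional on-treatment pregnancy testing may be performed at the investigator's discretion or as required per local laws and regulations".

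The other relevant places in the protocol are:

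- **Section 12.5.3** treats a woman as fertile from menarche to menopause unless she is permanently sterile. It then says: "Permanent sterilization methods include hysterectomy, bilateral salpingectomy, and bilateral oophorectomy". The list of premenopausal women who fall outside childbearing potential names the same three procedures, each of which must be documented.
- **Section 12.5.4.1** includes "bilateral tubal ligation/occlusion" among the highly effective contraceptive methods for women of childbearing potential.
- **Section 6.2, criterion 235** says that women of childbearing potential should enter only "the study after a confirmed menstrual period and a negative highly sensitive urine or serum pregnancy test". Criterion 237 excludes those with a positive serum test at screening.
- **Table 2-1** labels its testing row "Pregnancy test (FCBP only", where FCBP stands for females of childbearing potential.
- **Section 12.5.5.1** says that tests "must be performed for FCBP, including FCBP who commit to complete abstinence, as outlined below". It asks for two negative tests before lenalidomide and adds: "The subject may not receive lenalidomide until the Investigator has verified that the results of these pregnancy tests are negative".

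**The concern.** The note and the other sections give opposite instructions for a premenopausal woman with tubal ligation. A site that reads Section 9.2.4.1 would omit her tests. A site that reads Section 12.5.5.1 or Table 2-1 would do all of them.

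Pregnancy testing matters here because of lenalidomide, which the protocol links to embryo-fetal toxicity (Section 3.3.3) and for which it requires a pregnancy risk-minimization plan (Section 12.5.4.1). The note contradicts that safeguard where the protocol makes it mandatory, at the two tests that must be negative before the first lenalidomide dose. It also leaves criterion 237 unassessable, because that criterion depends on a screening test the note says is not needed.

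**Working it through.** The plan gives no figure on this point to reproduce. The check sets the sections side by side and then counts the tests at stake.

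**Step 1: is a premenopausal woman with tubal ligation of childbearing potential?** Yes.

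- The sentence on sterilization methods in Section 12.5.3 could be read as open-ended. The list that follows it is closed: a premenopausal woman must have had one of three named procedures, and ligation is not among them.
- Section 12.5.4.1 lists ligation as contraception for women of childbearing potential, which would be pointless if ligation removed them from that group.
- Section 12.5.4.2, on partners of male subjects, names ligation as an alternative to non-childbearing potential and so treats the two as different states.

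**Step 2: what does each place require of her?**

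| Place in protocol | Instruction | Exception for ligation? |
|---|---|---|
| 9.2.4.1 note | No protocol testing | The note is the waiver |
| 6.2, criterion 235 | Negative test before inclusion | None |
| 6.2, criterion 237 | Screening serum test; excluded if positive | None |
| Table 2-1 | Tests at screening, through treatment and at safety follow-up | None |
| 12.5.5.1 | Two negative tests before lenalidomide, then regular tests | None |
| 12.5.2.1 | Lenalidomide contraindicated unless she accepts the protocol's testing frequency | None |

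**Step 3: how many tests are at stake?** The inputs are Table 2-1 and Section 12.5.5.1, which confirms weekly testing over the first 28 days. Cycle 1 is taken as days 1, 8, 15 and 22. The count assumes that the woman completes all 12 cycles.

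- Before lenalidomide: screening 1 + cycle 1 day 1 (within 24 hours before the dose) 1 = **2**.
- Afterwards, regular menses: cycle 1 days 8, 15 and 22 = 3; cycles 2 to 12 at one per cycle = 11 × 1 = 11; safety follow-up 1. Sum 3 + 11 + 1 = **15**.
- Afterwards, irregular menses: 3; cycles 2 to 12 at two per cycle = 11 × 2 = 22; safety follow-up 1. Sum 3 + 22 + 1 = **26**.
- Totals: 2 + 15 = **17** (regular) and 2 + 26 = **28** (irregular).

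**Step 4: do the remaining provisions close the gap?** Not for the pre-treatment tests.

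- The discretionary sentence in Section 9.2.4.1 covers on-treatment tests only.
- The rule in Section 12.5.5.1 on testing after a missed period is reactive.
- Section 7.1.2.2.1 requires compliance with restricted distribution programs, but their testing rules are not in the documents, so they can be neither relied on nor dismissed.

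**The case against.** The strongest counter-argument is that the note is a deliberate, specific exception that overrides the general rule. Section 9.2.4.1 is the descriptive text for the Table 2-1 row, so a note there can be read as qualifying that row. Section 12.5.4.2 also gives tubal ligation special treatment, for partners of male subjects.

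This does not resolve the conflict. Even if the note qualifies Table 2-1, it leaves criteria 235 and 237 and Section 12.5.5.1 untouched, and none of them refers to it. The exception also runs against the protocol's own reasoning. Abstinence is on the same highly effective list as ligation, yet Section 12.5.5.1 expressly tests abstinent women, so using a highly effective method does not excuse testing. If the exception was intended, it would have to be written into those sections, so the text needs correcting either way.

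A second argument is that harm is unlikely in practice. Eligibility waivers are not given (Section 6), so a site may meet criterion 235 before it meets the note, and the distribution programs may impose tests of their own. Both are fair points. They make the omission conditional and the counts of 17 and 28 maxima, but they do not remove the contradiction.

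A third argument concerns cost. Appendix 3 (Section 12.3) sends amendments to ethics committees for approval where necessary, and about 100 sites are planned (Section 5.2.2). That is a reason to put the change into the next amendment and to send a clarification meanwhile. It is not a reason to keep the note.

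**Conclusion.** The concern holds. For a premenopausal woman with tubal ligation, the Section 9.2.4.1 note contradicts criteria 235 and 237, Table 2-1 and Section 12.5.5.1, and no text ranks them.

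The practical size is small. The documents do not say how many women are affected, but the median age at diagnosis of 69 years (Section 3.2.1) suggests few. Risk per woman is low: Section 12.5.4.1 puts failure of the listed methods below 1% per year with consistent and correct use, treatment lasts about 12 months, and a second method is required. At most 17 or 28 tests per woman would be omitted. This assumes 12 completed cycles, a site that relies on the note alone, and no testing from any other source. Sample size, power, type I error and all planned analyses are unaffected.

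The point still deserves correction because the possible harm is serious and irreversible and the remedy costs very little.

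**What to change.** Delete the tubal-ligation note from Section 9.2.4.1, so that women with ligation who are of childbearing potential under Section 12.5.3 are tested according to Section 12.5.5.1 and Table 2-1. Restricting the note to women who are permanently sterile or postmenopausal would also remove the conflict, but it adds nothing because those women are already outside the testing requirement. Until the protocol is next amended, send sites a short clarification to the same effect.

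The cost is one sentence of protocol text, the clarification, and, for the few women concerned, urine or serum tests already scheduled for other women of childbearing potential.

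A separate, lesser wording point can be settled at the same time: criterion 238 and Section 12.5.2.3 should say whether the ligation exception for partners of male subjects in Section 12.5.4.2 is intended. The main correction does not depend on it.
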